### **Statistical software**

Data analyses will be conducted using STATA software (StataCorp LP, College Station, Texas), Version 19.1.

## Illustrations

### Tables

Table 1. Baseline Characteristics.

	Physiotherapist-led exercise (n = )	Usual care (n = )	BetterHip Cohort (n = 120)
Biological Sex (Male/Female)			
Male, n (%)			
Female, n (%)			
Gender			
Male, n (%)			
Female, n (%)			
Specification, n (%)			
Age (years), mean (SD)			
Height (cm), mean (SD)			
Weight (kg), mean (SD)			
Body mass index (kg/m^2), mean (SD)			
FAI Morphology			
CAM, n (%)			
Pincer, n (%)			
Mixed, n (%)			
Alpha Angle, Mean (SD)			
Lateral Center Edge Angle, Mean (SD)			
Positive Crossover Sign, n (%)			
Acetabular Index Angle, Mean (SD)			
Index hip			
Left, n (%)			
Right, n (%)			
Bilateral symptoms			
No, n (%)			
Yes, n (%)			
Hip symptom duration			
0-1 years, n (%)			
1-2 years, n (%)			
2-5 years, n (%)			
> 5 years, n (%)			
Previous treatment due to hip symptoms			
Exercise, n (%)			
Physiotherapy, n (%)			
Chiropractor, n (%)			
Osteopathy, n (%)			
Medicine, n (%)			
Intra-articular steroid injection, n (%)			
Previous hip surgery			
Non-index hip, n (%)			
Educational level			
Primary school, n (%)			
Vocational education, n (%)			
High school or similar, n (%)			
Higher education, n (%)			
Employment status			
Student / Education, n (%)			
Working, n (%)			
Not working, n (%)			
Cohabitation status			
Married or cohabitating, n (%)			
Living alone, n (%)			
Smoking status			
Never, n (%)			
Former, n (%)			
Current, n (%)			

**Use of analgesics**

Paracetamol, n (%)  
NSAIDS, n (%)  
Morphine or opioids, n (%)  
Other, n (%)

**Comorbidities**

Specification (%), n (%)  
Specification (%), n (%)

**Physical activity level (SQUASH)**

Total activity score (METs)  
Light intensity (min/week)  
Moderate intensity (min/week)  
Vigorous intensity (min/week)

**Pain Kinesiophobia**

TSK-17 (17-68), mean (SD)

FAI: Femoroacetabular Impingement. NSAID: Nonsteroidal Anti-inflammatory Drugs. MET: Metabolic Equivalent.

SQUASH: the short questionnaire to assess health-enhancing physical activity. TSK-17: Tampa Scale of Kinesiophobia.

SD: Standard Deviation. 95% CI: 95% Confidence Interval. MET: Metabolic Equivalent.

If data is not normally distributed median and interquartile range (IQR) will be reported instead of the mean and standard deviation (SD).

**Table 2:** Changes from baseline to 6-month follow-up in primary and secondary outcomes in the intention-to-treat-population.

	Physiotherapist-led exercise (n = )			Usual care (n = )			Difference in change (95% CI)	
	Baseline (95% CI)	6-mo (95% CI)	Change (95% CI)	Baseline (95% CI)	6-mo (95% CI)	Change (95% CI)		
Primary								
iHOT-33, (0-100)								
Secondary								
1-RM Leg Press, Kg								
Index hip								
Non-index hip								
Hop for Distance, cm								
Index hip								
Non-index hip								
One-Leg Rise Test, Reps								
Index hip								
Non-index hip								
PASS (% Yes)								
GPE QoL								
GPE Pain								
GPE ADL								
Hip surgery (%)								

6-mo: 6-month follow-up. 95% CI: 95% Confidence Interval. iHOT-33: International Hip and Outcome Tool 33. 1 RM: 1 Repetition Maximum. Reps: Number of repetitions (0-50). PASS: Patient Acceptable Symptom State. GPE: Global Perceived Effect. QoL: Quality of Life.

**Table 3:** Changes from baseline to 6-month follow-up in the other outcomes in the intention-to-treat-population.

	Physiotherapist-led exercise (n = )			Usual care (n = )			Difference in change (95% CI)
	Baseline (95% CI)	6-mo (95% CI)	Change (95% CI)	Baseline (95% CI)	6-mo (95% CI)	Change (95% CI)	
iHOT-33 subscales, (0-100)							
Symptoms							
Sport							
Job							
Social							
HAGOS subscales, (0-100)							
Pain							
Sport							
Quality of Life							
SQUASH							
Total activity score (MET)							
Light intensity (min/week)							
Moderate intensity (min/week)							
Vigorous intensity (min/week)							
Sport participation							
HSAS, (1-8)							
RTS, (1-4)							
iHOT-33: International Hip and Outcome Tool 33. Symptoms: Symptoms and Functional Limitations. Sports and Recreational Activities. Job: Job-related concerns. Social: Social, Emotional, and Lifestyle Concerns. HAGOS-Sport: Physical Function in Sport and Recreation. 1 RM: 1 repetition maximum. Cm: centimeters. Kg: Kilograms. PASS: Patient Acceptable Symptom State. HAGOS: The Copenhagen Hip and Groin Outcome Score. SQUASH: the short questionnaire to assess health-enhancing physical activity. TSK-17: Tampa Scale of Kinesiophobia. HSAS: the Hip and Sports Activity Scale. RTS: Return to Sport questionnaire. SD: Standard Deviation. 95% CI: 95% Confidence Interval. MET: Metabolic Equivalent.							

**Table 4:** Costs and effects from baseline to 12-month follow-up in the intention-to-treat population.

	Physiotherapist-led exercise (n = )			Usual care (n = )			ICER/ICUR (95% CI)	
	Baseline (95% CI)	12-mo (95% CI)	Change (95% CI)	Baseline (95% CI)	12-mo (95% CI)	Change (95% CI)		
Effects								
QALYs								
iHOT-33, 0-100								
Healthcare costs (HUQ)								
Number of visits								
Physiotherapist								
General practitioner								
Allied health professional								
Complementary care provider								
Emergency department								
Medical specialist								
Admitted to the hospital								
Hip surgery								
Other healthcare providers								
Healthcare Costs (HUQ)								
Medicine usage								
Prescription 1								
Prescription 2								
Prescription 3								
Productivity Costs (IPCQ)								
Indirect costs								
Absenteeism								
Presenteeism								
Productivity loss								

QALY: Quality Adjusted Life Years. HUQ: Health care utilization questionnaire. IPCQ: The Productivity Costs Questionnaire. iHOT-33: International Hip and Outcome Tool 33. SD: Standard Deviation. 95% CI: 95% Confidence Interval. DKK: Danish Crowns.

**Table 5.** Incremental Cost-Effectiveness Ratios (ICERs), Incremental Cost-Utility Ratios (ICURs), and Distribution of the Joint Cost-Effect Pairs in the Cost-Effectiveness (CE) Plane.

Analysis	Mean cost difference (95% CI)	Mean effect difference (95% CI)	ICUR/ICER	Distribution in CE Plane (%)			
				NE	SE	SW	NW
Main analysis							
iHOT-33							
QALYs							
SA 1: Complete case analysis							
iHOT-33							
QALYs							
SA 2: Imputed data sets							
iHOT-33							
QALYs							
SA 3: Excluding Melbourne							
iHOT-33							
QALYs							

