### **Sample size calculation**

The sample size calculation is based on a clinical superiority calculation using data from a pilot RCT by Kemp et al. Kemp et al. found a mean change of 27 (SD 26) points on the iHOT-33 in their strength exercise group (e.g., intervention group) and a mean change of 11 (SD 8) points in their stretching group (e.g., control group) after 12 weeks of intervention (between-group difference of 16 [95% CI -9; 38] points). The superiority margin is a 6 points MCID in the between-group change on the iHOT-33. The estimated mean difference of 16 points, a superiority margin of 6 points, a SD of 19.2, a power of 80% and an alpha level of 5% results in a total sample size of n=94 (n=47 in each group). After allowing a dropout-rate of up to 28% our required sample size will be n=120 (n=60 in each group).

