The incremental cost-effectiveness ratio (ICER) and cost-utility ratio (ICUR) will be calculated by dividing the between-group difference in change in mean total costs by the difference in mean change for QALYs and iHOT-33 scores. The ICER and ICUR provide a measure of the additional cost per additional QALY, or iHOT-33 point gained or lost by physiotherapist-led exercise compared to usual care. The ICER and ICUR will be presented in Table 5. Bootstrapping techniques will be used to estimate the uncertainty surrounding the cost-effectiveness estimates. Cost-effectiveness planes (Figure 2) visually represent the differences in costs and health outcomes, and cost-effectiveness acceptability curves (Figure 3), graphically present the impact of uncertainty of the ICER and ICUR (the probability of the physiotherapist-led exercise intervention being cost-effective compared to usual care, with possible values of the cost-effectiveness threshold).

*Sensitivity analysis:*

Various one-way sensitivity analyses will be performed to test the robustness of the study results. First, a complete case analysis will be performed by using only cases with complete data for both outcomes and costs. 20 of the 120 patients enrolled in the study will be from Melbourne, Australia. A sensitivity analysis will be conducted, excluding the patients from Australia because of sample size disparity (100 in Denmark and 20 in Australia) and possible variations in healthcare practices, costs, and outcomes across countries.

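### Table 4 plans a 95% CI for the ICER/ICUR, which the text assigns to Table 5 without one and which has no usable meaning when the effect difference may be near zero

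*SAP*

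**What the plan says.** **Table 4 (SAP, Illustrations).** The table lists costs and effects from baseline to 12 months, and its last column is headed "ICER/ICUR (95% CI". The column runs beside every row: QALYs and iHOT-33, then nine types of healthcare contact, three prescriptions and three kinds of productivity loss.

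**Text (SAP, Health Economic Evaluation, base-case analysis and the paragraph after it).** The ratios are obtained by "dividing the between-group difference in change in mean total costs by the difference in mean change for QALYs and iHOT-33 scores". Their place is stated: "The ICER and ICUR will be presented in Table 5". On uncertainty: "Bootstrapping techniques will be used to estimate the uncertainty surrounding the cost-effectiveness estimates". The displays named are cost-effectiveness planes and "cost-effectiveness acceptability curves (Figure 3), graphically present the impact of uncertainty of the ICER and ICUR". No interval method for the ratio is given, and no rule for a zero or negative effect difference.

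**Table 5.** It has a 95% CI for the mean cost difference and one for the effect ("Mean effect difference (95% CI"), a ratio column without an interval, and four columns under "Distribution in CE Plane" for the NE, SE, SW and NW quadrants.

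**Tables 2 and 3.** The same last column holds the between-group difference in change with its 95% CI.

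**The concern.** A ratio of two differences has no consistent order once its denominator can change sign. A positive ICER can mean more effect at more cost, or less effect at less cost. A negative one can mean that exercise dominates usual care or is dominated by it. An interval on that scale mixes opposite decisions.

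Table 5 reserves columns for both quadrants with a negative effect, so the SAP itself allows for replicates on either side of zero.

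At stake is an interval, printed in one results table, that readers cannot interpret and that has no counterpart in the table meant for the ratios. The primary clinical analysis is not involved.

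**Working it through.** **1. Rows.** Of the 17 data rows in Table 4, 2 are effects. The other 9 + 3 + 3 = 15 are single resource or cost items with no effect denominator of their own, so the heading cannot apply to them.

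**2. One value, opposite meanings (illustrative differences).**
- +10,000 / +0.02 = +500,000 and −10,000 / −0.02 = +500,000 DKK per QALY.
- −10,000 / +0.02 = −500,000 (dominant) and +10,000 / −0.02 = −500,000 (dominated).

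**3. How often the denominator crosses zero.** The SAP gives no figure for this interval, so there is none to reproduce. For an effect difference d with standard error SE:
- share of replicates below zero, if d is the estimate: Φ(−d/SE);
- chance that the 95% CI for the effect includes zero, if d is the true value: Φ(1.96 − d/SE) − Φ(−1.96 − d/SE).

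Inputs:
- iHOT-33: SD 19.2 and 60 per arm, both from the sample size section, so SE = 19.2 × √(2/60) = 3.51. This assumes that the SD also holds at 12 months and that no one is lost.
- QALY: the SAP gives no SD. SE 0.02 is assumed, which at 60 per arm is an SD of 0.02 / √(2/60) ≈ 0.11.

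| Outcome | d | d/SE | Replicates below 0 | 95% CI includes 0 |
|---|---|---|---|---|
| QALY | 0.02 | 1.00 | 15.9% | 83% |
| QALY | 0.03 | 1.50 | 6.7% | 68% |
| QALY | 0.06 | 3.00 | 0.1% | 15% |
| iHOT-33 | 3 | 0.86 | 19.6% | 86% |
| iHOT-33 | 6.1 | 1.74 | 4.1% | 59% |
| iHOT-33 | 10 | 2.85 | 0.2% | 19% |
| iHOT-33 | 16 | 4.56 | 0.0% | 0.5% |

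Range for the QALY assumption at d = 0.03 and 60 per arm: SD 0.10, 0.15 and 0.20 give 5.0%, 13.7% and 20.6% of replicates below zero.

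**4. What a percentile interval would look like.** Assume a cost difference of 4,000 DKK (SE 3,000), independent of the effect.
- d = 0.02: point ratio 4,000 / 0.02 = 200,000 DKK per QALY; the 2.5th to 97.5th percentiles of simulated ratios run from about −1.9 to +2.2 million. P(cost difference < 0) = Φ(−1.33) = 9.1%. Negative ratios therefore mix 0.159 × 0.909 = 14.4% dominated with 0.841 × 0.091 = 7.7% dominant replicates.
- d = 0.03: about −0.9 to +1.3 million.
- d = 0.06: about −0.04 to +0.26 million.

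**5. Would another method rescue the column?** The Fieller set contains the ratios R with (ΔC − RΔE)² ≤ 1.96² × (SE_C² + R² × SE_E²), taking costs and effects as uncorrelated. It is a bounded interval only if |ΔE| / SE_E > 1.96, that is, when the 95% CI for the effect excludes zero. Otherwise it is unbounded or in two pieces and cannot be printed as a lower and an upper limit.

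**6. Coverage.** In a simulation with 60 per arm, QALY SD 0.15 or iHOT-33 SD 19.2, and a cost difference of 10,000 DKK with SD 30,000, percentile intervals covered the true ratio in 92.6% to 97.6% of trials. Fieller sets stayed at about 95%. The fault lies in what the interval means, not in a gross loss of coverage.

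**The case against.** The best defence is that the header is a template slip. Tables 2 and 3 have a difference in change in the same position, and 15 of the 17 rows cannot hold an ICER. The text also assigns the ratios to Table 5, where the reporting is sound. This stands, and it makes the point small. It does not make the header harmless: an analyst who fills in the shell as printed would still produce the interval.

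Three stronger readings are tempting, and the document does not support them.
- *The SAP plans percentile intervals of bootstrapped ratios.* It says only that bootstrapping will be used for uncertainty, and then names planes and curves. The percentile figures above are an illustration. The problem survives because the Fieller set fails as a single interval in the same situation.
- *The main economic result would carry wrong error bars.* The ratios belong in Table 5, without an interval and beside the CIs for both differences and the quadrant shares. Planes and curves are planned as well, so any crossing of zero would be visible.
- *The ratio's interval is always unusable.* The sample size section assumes "The estimated mean difference of 16 points, a superiority margin of 6 points". At 16 points, practically no iHOT-33 replicates cross zero. At an assumed QALY difference of 0.06, only 0.1% do.

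**Conclusion.** The Table 4 column is wrong as written. It conflicts with the text and with Table 5, it cannot apply to most of its rows, and it promises an interval that is not interpretable when the effect difference may be near or below zero. For QALYs that condition is plausible, but the shares depend on assumed differences and standard errors that the SAP does not give. For iHOT-33 it arises at differences of about 6 points or less, given the planning SD, and not at 16. The correction is a minor one to reporting. The point ratios, the Table 5 results and the clinical conclusions do not change.

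**What to change.** - Replace the last heading of Table 4 with the between-group difference (95% CI), matching Tables 2 and 3.
- Keep the point ICER and ICUR in Table 5 only, beside the CIs for the cost and effect differences.
- State that uncertainty in the ratios is shown only by the quadrant shares, the plane and the acceptability curve.
- Because the quadrant shares then carry weight, correct the Table 5 note. It makes north the more costly side for NE and SE, but calls SW more costly and NW less costly.
- Optional: add incremental net monetary benefit with a 95% CI at the thresholds on the acceptability curve. It comes from the same replicates, and much of its information is already in the curve.

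The cost is an edit to a table shell, its note and one sentence of text. No new data or analysis is needed, apart from the optional item.

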aAnalyzed using linear regression. b $\beta$ , Regression coefficient. The interpretation of the crude and adjusted  $\beta$  is the change in the dependent variable for every unit of each of the independent variables. cAdjusted each of the independent variables (i.e., Adherencesupervised, AdherenceTotal, Exercise Volume, Biological Sex, Age, and Physical Activity Level). dDependent variable in each respective regression model. [95% CI]: 95% confidence interval. (p): P-value. iHOT-33: International Hip and Outcome Tool 33.

## Figures

[figure not shown]
Figure 1. CONSORT Flowchart in The Better Hip Trial.

[figure not shown]
**Figure 2.** Visualization of changes in iHOT-33 score in the physiotherapist-led exercise group and the usual care group at baseline, 3- and 6-month follow-up with 95% Confidence Intervals. (Example, not based on data).

**Figure 3.** Cost-effectiveness (CE) plane for iHOT-33 and QALYs.

**Figure 4.** Cost-effectiveness acceptability curve for iHOT-33 and QALYs change (Example, not based on data).

